7.3. Secondary Endpoints

All secondary analyses will be conducted in an exploratory fashion with p-values and confidence intervals presented as descriptive statistics with no adjustments for multiple comparisons. Interval estimates will be generated at the 95% confidence level. Analyses will be conducted on the ITT population and the PP populations. Missing data will not be imputed.

7.3.1. Pulmonary Vascular Resistance

Endpoint: A right heart catheterization (RHC) will be performed at Screening and Week 24. Data for the RHC will be collected on the Right Heart Catheterization CRF page.

During a RHC a catheter is guided to the right side of the heart and then into the pulmonary artery; blood flow through the heart is observed and is used to measure pressures in a subject's heart and lungs. Pulmonary vascular resistance (PVR) will be collected in Wood Units and method of cardiac output (indirect or estimated Fick, direct Fick, or thermodilution) will be collected as well. Multiple types of PVR (indirect or estimated Fick, direct Fick, or thermodilution) may be collected for a subject. Higher PVR values indicate worse disease status.

PVR will be derived in two ways:

1. First, as noted previously, multiple types of PVR (indirect Fick, direct Fick, or thermodilution) may be collected for a subject. The PVR value used for analysis will be chosen in the following order, as available from the Right Heart Catheterization CRF page: 1. thermodilution, 2. direct Fick, 3. indirect Fick. Both the screening and Week 24 RHC must use the same method of cardiac output. If the method used for screening and Week 24 do not match, only the baseline measure will be included in model-based analyses.
2. Second, PVR will be derived using the formula:

$$PVR = (mPAP - PCWP)/CO, \text{ where}$$

mPAP = mean pulmonary artery pressure (mmHg)

PCWP = mean pulmonary capillary wedge pressure (mmHg)

CO = Cardiac Output (L/min)

Similar to the first method, method of cardiac output will be chosen in the following order, as available: 1. thermodilution, 2. direct Fick, 3. indirect Fick. PCWP can be recorded at end expiration or by a computer-generated mean. If both are recorded, at end expiration will be used.

For each derived PVR variable, change from Screening to Week 24 in the PVR and percent change from Screening to Week 24 in the PVR will be computed for each subject. Missing values will not be imputed.

Analysis: For each derived PVR variable, the following analyses are planned.

1. Descriptive statistics will be presented for PVR, percent change from Screening, and change from Screening in PVR for each treatment group and overall. Spaghetti plots and summary statistics including 25th percentile, mean, median, and 75th percentile will be plotted for each visit by treatment group. Separate summaries will be prepared for all subjects with available data at either time point and for the subset of subjects with measurements at both time points.
2. Additionally, a repeated measures mixed model will be fit with PVR as the outcome and treatment, visit week (actual observed week), and their interaction as predictors. Random intercepts and slopes will be fit for each subject using an unstructured covariance structure for each treatment group. Model estimates and standard errors for PVR and change from baseline in PVR will be presented at baseline and Week 24, along with the differences between arms. An appropriate contrast will be used to test the difference (baseline to Week 24) between treatment arms.

A separate analysis is planned to simultaneously evaluate the all reported PVR (indirect Fick, direct Fick, or thermodilution) measures for a subject without the prioritization rules described above. A multivariable repeated measures mixed model will be fit with PVR as the outcome and treatment, type of PVR (indirect or estimated Fick, direct Fick, or thermodilution), visit week (actual observed week) and interaction terms for type*treatment and type*treatment*week. Random intercepts and slopes will be fit for each subject using an unstructured covariance structure for each PVR type and treatment group. In addition, separate residual variance components will be estimated for each type of PVR.

Note: PVR is measured only at screening and Week 24. Subjects lost prior to Week 24 will contribute only screening data. If subjects are not lost completely at random, findings from these analyses may be biased as they will reflect changes in PVR in the subset of individuals who made it to Week 24.

Analogous analyses will be repeated on the percent change from Screening in PVR at Week 24.

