6.5.4.6 Week 24 ± 7 days (Visit 10)

Assessments:

- Full Physical Examination with Vital Signs
- NYHA Functional Class Assessment
- Right heart catheterization: The subject should be on the same amount of supplemental oxygen used during the Screening RHC unless safety will be impacted. The methods of calculating pulmonary capillary wedge mean pressure and cardiac output should be the same as that used for the Screening RHC and, if feasible, the procedure should be scheduled at approximately the same time of day as the Screening RHC.
- Pulmonary Function Tests: DLCO only
- Oxygen Saturation (forehead or ear probe must be used for saturations < 95% by finger probe). Measure first at room air, then add/titrate oxygen if needed to maintain O₂ saturation ≥ 90%. The room air oxygen saturation measurement will be conducted at the discretion of the study physician. The measurement should not be performed if subject safety will be compromised.
- SF-36
- SHAQ

- 6MWT: The subject should complete the assessment with the same amount of supplemental oxygen used to complete the Screening 6MWT unless safety will be impacted (if the 6MWD *decreased* from the Screening 6MWD by more than 20%, repeat the 6MWT within 7 days, but not on the same day)
- Digital Ulcer Count
- Hematology: CBC with differential count and platelet count (hematocrit, hemoglobin, platelets, WBC, bands, eosinophils, lymphocytes, monocytes, neutrophils)
- Chemistry: albumin, alkaline phosphatase (ALP), ALT/SGPT, AST/SGOT, BUN, creatinine, potassium, sodium, total and indirect bilirubin, total CO₂, total protein, BNP/NT-proBNP
- CD19+ B cell studies
- Autoantibodies
- Serum Immunoglobulins
- IL-1, IL-6, and other cytokine assays
- HACA and rituximab serum level (PK). Batched and sent to Covance Laboratories.
- Concomitant Medication Assessment
- Adverse Event Assessment

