- ¹⁰ Infectious Disease Screen: HIV antibody, hepatitis B surface antibody and surface antigen, HCV antibody with HCV RNA (PCR) if antibody positive.
- ¹¹ Pregnancy Test: For women of child-bearing potential a pregnancy test (urine or serum per institutional policy) must be obtained at screening and within 72 hours of each rituximab infusion.
- ¹² CD19+ B Cell Studies: Blood sent to Stanford Human Immune Processing Center for the Stanford Human Immune Monitoring Center.
- ¹³ Autoantibodies: will include but are not limited to Anti-U1 RNP, anti-U3 RNP, anti-B23, anti-cardiolipin, anti-Th/To, anti-CENP-B, and RF. Frozen serum sent to University of Pittsburgh Immunoassay Core Laboratory.
- ¹⁴ Serum Immunoglobulins: Quantitative Immunoglobulin Levels including IgG subclasses (frozen serum sent to Stanford Human Immune Processing Center for the Stanford Human Immune Monitoring Center).
- ¹⁵ IL-1, IL-6, and Other Cytokine Assays: Frozen serum sent to Stanford Human Immune Processing Center for the Stanford Human Immune Monitoring Center.
- ¹⁶ Rituximab: Per Protocol Section 5, *Treatment of Subjects*.
- ¹⁷ Vaccinations: All immunizations must be completed at least 4 weeks prior to starting rituximab/placebo. Subject must be vaccinated with the pneumococcal vaccine at least 4 weeks prior to initiation of therapy, unless subject was vaccinated within 5 years of study entry. If vaccination occurred greater than 5 years prior to study entry, the subject must be revaccinated at least 4 weeks prior to initiation of therapy. Depending on the season, influenza vaccine should be administered at least 4 weeks prior to dosing with rituximab/placebo. Otherwise, it should be administered as late as possible in the flu season to still be effective after the last dose of rituximab/placebo.
- ¹⁸ The 6MWT must be completed within 14 days of the first treatment visit (Day 0).
- ¹⁹ HACA and PK Assays: HACA and rituximab serum level (PK). Batched and sent to Covance Laboratories.
- ²⁰ When completing the repeat RHC, the subject should be on the same amount of supplemental oxygen used during the Screening RHC unless safety will be impacted. The method of calculating cardiac output should be consistent with that used at the Screening RHC.

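### SAP 7.3.1 selects the wedge reading for derived PVR without requiring the same method at both visits, so a method difference can enter an individual subject's PVR change even where a matched pair exists

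*SAP*

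**What the plan says.** SAP 7.3.1 derives PVR in two ways. The first takes the PVR recorded on the catheterisation CRF page. The second computes (mPAP - PCWP)/CO, and for its wedge term states: "PCWP can be recorded at end expiration or by a computer-generated mean. If both are recorded, at end expiration will be used". Nothing in that rule refers to the other visit.

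Cardiac output is treated differently. Under the first derivation the SAP says "Both the screening and Week 24 RHC must use the same method of cardiac output", and it gives the consequence of a mismatch: "If the method used for screening and Week 24 do not match, only the baseline measure will be included in model-based analyses". The second derivation carries the cardiac output order over ("Similar to the first method, method of cardiac output will be chosen in the following order, as available"). Wedge pressure has neither a matching condition nor a stated consequence.

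The selected values feed directly into the endpoint: "For each derived PVR variable, change from Screening to Week 24 in the PVR and percent change from Screening to Week 24" are computed for each subject. The mixed model for each derived variable has treatment, visit week and their interaction as predictors, with no term for wedge method.

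On conduct, protocol 6.5.4.6 covers both inputs: "The methods of calculating pulmonary capillary wedge mean pressure and cardiac output should be the same as that used for the Screening RHC". Footnote 20 to protocol Table 6.1, repeated in SAP 13.2, mentions only one of them: "The method of calculating cardiac output should be consistent with that used at the Screening RHC". SAP section 11, which lists departures from the protocol, says nothing about wedge method.

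**The concern.** Derived PVR has two inputs whose measurement method can vary, cardiac output and wedge pressure. The protocol asks for both to be held constant within a subject. The SAP turns only the cardiac output half into an analysis rule.

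The gap goes beyond missing detail, because the stated preference can itself produce the mismatch. Suppose both wedge readings exist at Screening and only the computer-generated mean at Week 24. A same-method comparison is available from the two computer means. The rule as written instead takes the end-expiratory reading at Screening and the computer mean at Week 24. The change and percent change for that subject then contain the difference between two ways of reading the same pressure, and nothing in the model can separate it from a change in resistance.

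**Working it through.** The plan states no figure on this point, so there is none to reproduce. The check is algebraic.

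**Inputs from the documents**
- PVR = (mPAP - PCWP)/CO (SAP 7.3.1).
- Mean baseline PVR of enrolled subjects: 553 dyne-s/cm5 (protocol 8.1), which is 553/80 = 6.91 Wood units.
- SD of change in PVR: 350 dyne-s/cm5 (protocol 8.1, a planning value from the design used through protocol version 5.0).

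**Assumed inputs (not in the documents)**
- Difference between the two wedge readings: d = 1-6 mmHg.
- Cardiac output: 4-6 L/min.
- Share of subjects with a method switch: 10-30%.

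**1. Shift in one affected subject.** With mPAP and CO unchanged, a switch moves PVR by d/CO.

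| d (mmHg) | CO (L/min) | Shift (Wood units) | % of 6.91 |
|---|---|---|---|
| 1 | 6 | 1/6 = 0.17 | 2.4 |
| 3 | 6 | 3/6 = 0.50 | 7.2 |
| 3 | 4 | 3/4 = 0.75 | 10.8 |
| 5 | 4 | 5/4 = 1.25 | 18.1 |
| 6 | 4 | 6/4 = 1.50 | 21.7 |

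**2. Worked case (assumed values).** Take mPAP 40 mmHg and CO 4.0 L/min at both visits. Screening has end-expiratory 12 and computer mean 9; Week 24 has computer mean 9 only.
- Rule as written: Screening (40 - 12)/4 = 7.00; Week 24 (40 - 9)/4 = 7.75. Change +0.75 Wood units, or 0.75/7.00 = +10.7%, with no haemodynamic change.
- Computer mean at both visits: 7.75 and 7.75. Change 0.

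**3. Effect on the group comparison.** Let a be the shift and f the share of subjects affected. If switches are unrelated to arm and equally likely in either direction, the variance of change rises by f x a^2. Take the largest shift above, 1.5 Wood units = 120 dyne-s/cm5:
- f = 10%: SD = sqrt(350^2 + 0.1 x 120^2) = 352, or +0.6%.
- f = 30%: SD = sqrt(350^2 + 0.3 x 120^2) = 356, or +1.7%.
- If the true SD were 200 instead, f = 10% gives sqrt(200^2 + 0.1 x 120^2) = 203.6, or +1.8%.

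If the switches all run in one direction, each arm's mean change moves by f x a: 0.1 x 120 = 12 dyne-s/cm5 at 10% and 0.3 x 120 = 36 at 30%. With equal f this cancels between arms but stays in each arm's change from baseline. If f differs by arm, the contrast is biased by the difference in f times a.

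**The case against.** The strongest reply is that conduct already deals with this. Protocol 6.5.4.6 tells sites to keep the wedge method the same, so a mismatch needs a departure from that instruction or uneven recording, and the documents do not show how often either occurs. This stands as to frequency. It does not remove the gap: the instruction is a recommendation, and no analysis rule carries it out.

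It can also be said that visit-by-visit selection is inferred. That is fair: the SAP is silent on matching and does not rule it out. Still, visit-by-visit is the natural reading, and a programmer following the text would implement it.

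A reader might go further than the documents allow in four ways.

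- **That the treatment comparison is biased.** Treatment is masked and randomised 1:1 (protocol 3.1.1), and nothing suggests that switching differs by arm. Without that, the result is a little noise.
- **That the artefact is as large as a clinically significant effect.** The 20-30% in protocol 8.1 belonged to the PVR primary endpoint used through version 5.0, since replaced by 6MWD, and it described a group effect. The 2-22% here is a shift in one affected subject. Protocol 5.7.1 does use a 20% rise in PVR for individuals, but as a sign of deterioration after Week 24, not as an analysis threshold. Among the cases in the table, only 6 mmHg with CO 4 L/min exceeds 20%.
- **That the rule creates mismatches even at fully compliant sites.** A site that used both methods at Screening and one at Week 24 has arguably not kept its methods the same.
- **That the SAP or footnote 20 contradicts the protocol.** Both are silent on matching wedge method; neither says anything opposed to 6.5.4.6.

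**Conclusion.** The gap is real but limited. As written, SAP 7.3.1 can pair an end-expiratory wedge pressure at one visit with a computer-generated mean at the other when a same-method pair exists. In an affected subject this shifts derived PVR change by d/CO: 0.17-1.5 Wood units, or about 2-22% of the enrolled baseline mean, under the assumed ranges for d and CO. The number of such subjects cannot be told from the documents.

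The 6MWD primary analysis is untouched. The affected results are those of derived PVR, a secondary endpoint whose p-values the SAP treats as descriptive. Individual changes, percent changes, the spaghetti plots and within-arm changes from baseline carry the artefact directly. The between-arm contrast loses little precision: at the largest assumed shift, the SD goes from 350 to 352-356 dyne-s/cm5. It is biased only if switching differs by arm. The case for acting is that the main repair costs almost nothing and follows the principle that the SAP already applies to cardiac output.

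**What to change.** In the second derivation of SAP 7.3.1, replace the wedge selection rule with a within-subject one: use end-expiratory PCWP if it is recorded at both Screening and Week 24; otherwise use the computer-generated mean if that is recorded at both. This needs SAP wording and a small programming change. It requires no new data and discards none.

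Where the two visits share no wedge method, flag the pair and report the PVR analysis with and without those Week 24 values. Dropping them outright, as the SAP does for a cardiac output mismatch, is a debatable trade. Losing 10% of Week 24 values raises the standard error by about 5% (1/sqrt(0.9) = 1.054), and losing 30% by about 20% (1/sqrt(0.7) = 1.195). Both exceed the noise computed above, and SAP 7.3.1 already warns of possible bias from subjects without Week 24 PVR.

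The change does not reach the first derivation, where the PVR value is taken as recorded and also has no wedge-matching rule; a sentence acknowledging this would be enough. Footnote 20 can be aligned with protocol 6.5.4.6 by naming the wedge method, as an editorial change.

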7.1.2. Assessment Time Windows

Allowable visit windows for all scheduled visits are provided in Table 7-1.

Table 7-1 Visit Windows

Visit	Window
Screening	-28 Days
Baseline	-7 Days
Day 0	
Week 2	± 4 Days
Weeks 4, 8, 12, 16, 20, 24, 28, 32, 36, 40, 44, 48	± 7 Days
Quarterly Monitoring	± 14 Days

Unscheduled visits may also occur throughout the study. All data will be included in analyses, regardless of time of assessment.

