11. CHANGES TO THE ANALYSES PLANNED IN THE PROTOCOL

[figure not shown]
1. Section 7.2.2: Primary endpoint:
 - a. Actual values rather than change from baseline in 6MWD will be used in the model.
 - b. Remove baseline measures of 6MWD as covariate
 - c. Use visit week rather than visit day
 - d. Addition of quadratic term for visit week
 - e. Remove limitations from musculoskeletal disease as a covariate. The number of “yes” occurrences is too sparse to inform the analysis.
2. Section 7.3.3: Clinical worsening: Protocol says “worsening of 6MWD by > 20% and a decrease in functional class” vs. corrected “worsening of 6MWD by > 20% and an increase in functional class”
3. Section 7.3.4: Analyses changed from using a logistic regression model to analyzing time to first change or addition of PAH medications.

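### SAP 7.3.1 drops the protocol's baseline-adjusted ANCOVA for PVR without listing the change, which costs some precision, and extends to percent change a model that does not suit it

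*SAP*

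**What the plan says.** Protocol 8.3.2.2 plans one method for both PVR endpoints (change, and percent change, from baseline to Week 24): ANCOVA with treatment, cardiac-output method and baseline PVR.

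SAP 7.3.1 contains no ANCOVA. After descriptive summaries it says "a repeated measures mixed model will be fit with PVR as the outcome and treatment, visit week (actual observed week), and their interaction" as predictors, and adds: "Random intercepts and slopes will be fit for each subject using an unstructured covariance structure for each treatment group". For the relative endpoint it says only: "Analogous analyses will be repeated on the percent change from Screening in PVR at Week 24".

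Protocol 8.5.6 promises that major changes from the protocol will be noted in the SAP. SAP Section 11 is the list of such changes. It has three numbered items, for 7.2.2, 7.3.3 and 7.3.4, and none for 7.3.1. The last reads: "Analyses changed from using a logistic regression model to analyzing time to first change or addition of PAH medications".

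Protocol 8.3.4 still refers to an ANCOVA result when it subsets the agreement analysis. It also repeats the PVR analysis for PVRf and treats PACf in the same way. SAP 7.3 states the status of all of this: "All secondary analyses will be conducted in an exploratory fashion".

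**The concern.** Change and percent change in PVR are named secondary endpoints. The SAP models screening PVR as an outcome, with a free mean in each arm, and not as a covariate. A chance difference between arms at screening is therefore not adjusted for, although the protocol planned that adjustment and the value is already collected. In a trial of 60, that gives up precision for nothing.

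The reporting gap matters because Section 11 records closely similar changes elsewhere: removal of the baseline 6MWD covariate for the primary endpoint, and a change of model for PAH medication changes. A reader comparing protocol and report would find a different PVR analysis with no explanation.

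For percent change there is also a question of fit. A random-slope model needs repeated values that vary, and percent change from screening supplies only one per subject.

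**Working it through.** **Inputs.** 30 subjects per arm, and 24 after 20% dropout (protocol 8.1; the dropout rate is stated there for 6MWD and applied to PVR as an assumption). SD of change in PVR 350 dyne-s/cm5 (protocol 8.1, superseded PVR design). The correlation rho between screening and Week 24 PVR is not in the documents; 0.5, 0.7 and 0.9 are assumed.

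**1. The plan's own PVR figure.** Protocol 8.1 gives 85% power with 80 subjects. The difference is 0.30 x 810 = 243 and the SE is 350 x sqrt(2/40) = 78.3. At an assumed two-sided 0.05, power is 86.6% (noncentral t). With the 251 also given there, it is 88.6%. The figure is broadly reproduced and is not disputed. It shows that 350 is the SD of an unadjusted change.

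**2. What the SAP contrast estimates.** With complete data at two common times, treatment, week and their interaction fit the four arm-by-time means exactly. The baseline-to-Week-24 contrast is then the unadjusted difference in mean change (0.386 against 0.386 in a simulated data set). With actual visit weeks it stays close: in simulated trials its correlation with the simple change difference was at least 0.98.

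**3. Precision, 30 complete per arm, equal variances.** Unadjusted SE = SD x sqrt(2/n) = 350 x sqrt(2/30) = 90.4. ANCOVA SE = that x sqrt((1 + rho)/2).

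**4. Precision, 30 screened and 24 completing per arm, loss at random.** The SAP model keeps screening-only subjects, so its SE is approximately 350 x sqrt(2 x [(1 + rho)/(2 x 24) + (1 - rho)/(2 x 30)]). ANCOVA on completers has SE 350 x sqrt(2/24) x sqrt((1 + rho)/2), with 350 x sqrt(2/24) = 101.0.

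| rho | Unadjusted, n = 30 | ANCOVA, n = 30 | Ratio | SAP-type, 24 of 30 | ANCOVA, n = 24 | Ratio |
|---|---|---|---|---|---|---|
| 0.5 | 90.4 | 78.3 | 0.87 | 98.5 | 87.5 | 0.89 |
| 0.7 | 90.4 | 83.3 | 0.92 | 99.5 | 93.1 | 0.94 |
| 0.9 | 90.4 | 88.1 | 0.98 | 100.5 | 98.5 | 0.98 |

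Scaling the SD to the enrolled baseline mean (350 x 553/810 = 239, an assumption) changes the SEs but not the ratios.

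**5. Unequal variances.** Let k be the Week 24 variance over the screening variance. With complete data the ratio of variances is k(1 - rho^2)/(1 + k - 2 rho sqrt(k)). Over rho 0.5 to 0.9 the SE ratio is 0.81 to 0.89 at k = 0.8, and 0.91 to 1.00 at k = 1.25. The gain therefore vanishes at k = 1.25 with rho 0.9.

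**6. Percent change.** The model has seven variance parameters: three per arm plus a residual. Each subject has one informative value, at Week 24. If the screening zeros are included, the result depends on the origin of visit week, which SAP 7.3.1 does not state.

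- *Weeks from each subject's own screening.* All 60 zeros fall at week 0 and are fitted exactly by the arm intercepts. As the intercept and residual variances shrink together, -2 REML log-likelihood falls by (60 - 2) x ln(variance ratio). From 1 to 1e-8 that is 58 x ln(10^8) = 1068. A simulated data set (SD 45% assumed) went from 765 to -303, the same 1068. The likelihood is unbounded.
- *Weeks from Day 0.* Screening dates differ, so the zeros cannot all be fitted exactly, and the optimum is finite (797 to 883 in five simulated data sets). The model is nevertheless describing values that are zero by construction.

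ANCOVA on the single Week 24 value has neither problem. Its SE was 0.90 to 1.00 of the unadjusted SE in simulated lognormal PVR data.

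**The case against.** The best defence is that little is lost. The analysis is exploratory, the contrast is unbiased, and the change follows the one disclosed for 6MWD. The mixed model also keeps subjects whom a completers-only ANCOVA drops. All of that stands, and it is why the ratios for 24 of 30 completing are the fairer ones where there is dropout. It does not explain why Section 11 is silent, and a longitudinal model can keep those subjects and still adjust for baseline.

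Several stronger readings are tempting, and the documents do not support them.

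- *The percent-change model cannot be fitted.* The SAP specifies actual observed week, which rules out a common scheduled time, and Table 7-1 places Screening relative to Day 0. Day 0 is the more natural origin, and there the fit is finite. The sentence can also be read as a single comparison at Week 24, but then the SAP names no model for it.
- *The absolute PVR comparison is invalid.* With two visits per subject the variance components are separated only by scatter in visit dates, so fits on the boundary are likely. The treatment contrast stays close to the simple difference in change.
- *Dropping the cardiac-output method term does harm.* SAP 7.3.1 requires: "Both the screening and Week 24 RHC must use the same method of cardiac output". No harm is shown.
- *PVRf and PACf are left without a model.* Protocol 8.3.4 can be read as pointing to its own ANCOVA. One clarifying sentence is enough.
- *Early catheterisations are discarded.* The SAP note says "Subjects lost prior to Week 24 will contribute only screening data", while protocol 3.1 and 6.5.6 seek a catheterisation at an early endpoint and SAP 7.1.2 says "All data will be included in analyses, regardless of time of assessment". This is a wording point: the note fits subjects with no second catheterisation.

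**Conclusion.** The concern holds as a moderate point about documentation, precision and model fit. The protocol's ANCOVA was replaced, baseline adjustment was lost, and the change is not listed where protocol 8.5.6 leads a reader to expect it.

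For absolute PVR the cost is precision only, roughly 2% to 13% of the standard error under equal variances. That rests on assumed correlations of 0.5 to 0.9, and the gain can be near zero if the Week 24 variance exceeds the screening variance. For percent change the random-slope model is unsuitable under either time origin: unbounded under one, and fitted to fixed zeros under the more natural one.

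A reader might infer a threat to the trial's main result. There is none: these are exploratory secondary analyses, and the primary 6MWD test does not use them.

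**What to change.** In SAP 7.3.1:

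- (a) Restore the protocol's ANCOVA (treatment, baseline PVR, cardiac-output method) for change in PVR, and use ANCOVA on the single Week 24 value for percent change.
- (b) If screening-only subjects are to contribute to the absolute PVR analysis, use a constrained longitudinal model: one screening mean common to both arms, categorical visit, and an unstructured 2x2 covariance. The common mean is essential, because with free arm means the model returns the unadjusted difference in complete data. State how early-endpoint catheterisations are handled, since a categorical Week 24 visit would otherwise absorb them.
- (c) State that PVRf and PACf use the same model as (a).
- (d) List any remaining departure from protocol 8.3.2.2 in Section 11.

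The cost is SAP wording only. Item (a) returns to the method already in the protocol, and no new data are needed.
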